### **10.3. Metabolic Assessments**

Descriptive statistics will be presented by treatment group and visit for the observed and change from OL baseline values for the following metabolic assessments: HOMA-IR (in subjects not taking insulin and fasting), glucose tolerance (as measured by the post-GTT load glucose levels), fasting lipid panel (including total cholesterol, LDL, triglycerides, and HDL), and HbA1c (stratified by subjects with and without diabetes mellitus). Percent change from baseline will also be summarized for all parameters except HbA1c.

The above summaries will be repeated for the change from baseline (Day 1) to Month 12 in each of the metabolic assessments.

### **10.4. Weight, Waist Circumference, BMI, Total Lean Mass, Total Fat Mass, and Total Body Mass**

Descriptive statistics will be presented by treatment group and visit for the observed and change from OL baseline values for weight, waist circumference, BMI, percent total fat mass, total lean mass, and total body mass. Both absolute and percent change from OL baseline will be presented for weight.

The above summaries will be repeated for the change from baseline (Day 1) to Month 12 in weight, waist circumference, BMI, and percent total fat mass, total lean mass, and total body mass.

In the subset of subjects classified as overweight or obese ( $BMI \geq 25 \text{ kg/m}^2$  at baseline), the number and percentage of subjects achieving a greater than 5 percent reduction in total body weight from baseline to Month 12 will also be presented by treatment group.

### **10.5. Menstrual Regularity**

Menstrual regularity (in female subjects of childbearing potential who are not on hormonal or intrauterine device contraceptives) will also be summarized for the OL period. The number and percentage of subjects meeting the definition for having regular menstrual cycles (as defined in Section 9.5.5.) from OL baseline to Month 12 will be summarized by treatment group. This summary will be stratified based on menstrual cycle regularity at study entry.

In addition to the above summary, for premenopausal women assigned to the placebo group for the DB period (not using hormonal or IUD contraception), the number of menstrual periods from Week 24 to Month 12 will be compared to the number of menstrual periods from Day 1 to Week 24. The change in the number of menstrual periods between the two treatment periods will be summarized descriptively.

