#### **4.5. Exploratory Efficacy – OL Period**

Exploratory efficacy endpoints in the OL period include:

- percent change from baseline and OL baseline in glucocorticoid daily dose (in hydrocortisone equivalents adjusted for BSA [mg/m^2/day]) at Month 12, while Month 12 androstenedione values are adequately controlled at  $\leq 120\%$  of baseline or  $\leq$  ULN for age and sex
- achievement of a reduction in glucocorticoid daily dose to physiologic levels at Month 12
- change from baseline and OL baseline in hormone parameters (androstenedione, 17-OHP, ACTH, total testosterone, FSH, LH, progesterone, SHBG) at Month 12
- change from baseline and OL baseline in metabolic laboratory parameters (glucose tolerance [as measured by the post-GTT load glucose levels; in subjects without diabetes mellitus], HOMA-IR [in fasting subjects not on insulin], total cholesterol, LDL, HDL, HbA1c, triglyceride) at Month 12
- change and percent change from baseline and OL baseline in weight at Month 12
- change from baseline and OL baseline in BMI at Month 12

- change from baseline and OL baseline in waist circumference at Month 12
- change from baseline and OL baseline in percent total fat mass at Month 12
- change from baseline and OL baseline in total lean mass at Month 12
- change from baseline and OL baseline in total body mass (via DXA) at Month 12
- change from baseline and OL baseline in urine androgen metabolite levels at Month 12
- change from baseline and OL baseline in BMD at Month 12
- change from baseline and OL baseline in hirsutism (female subjects only) at Month 12
- change from baseline and OL baseline in acne (female subjects only) at Month 12
- change from baseline and OL baseline in bone markers (serum osteocalcin, serum bone-specific alkaline phosphatase, serum C-terminal telopeptide [CTX], urine N-terminal telopeptide [NTx]) at Month 12
- change from baseline and OL baseline in testicular adrenal rest tumor (TART) volume (expressed as a percentage of the total testicular volume) at Month 12 (male subjects only)
- change from baseline in menstrual regularity (premenopausal female subjects not using hormonal or IUD contraception only) at Month 12
- change in number of menstrual periods (premenopausal female subjects assigned to the placebo group for the DB period, not using hormonal or IUD contraception) at Week 24 to Month 12, compared to Day 1 to Week 24

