## 5.2. Week 24 (DB Period) Final Analysis

The final unblinded analysis of the double-blind, placebo-controlled period will be conducted once all subjects have had the opportunity to complete the Week 24 visit. Data through Week 24, including the primary, key secondary, secondary, and exploratory endpoints, will be analyzed. At this time, an analysis of all available safety and efficacy data through Month 12 will also be performed. Following this analysis, the subject, investigator, all study center personnel, and Sponsor personnel with direct contact with the site will continue to be blinded to the subject's blinded treatment assignment. All planned analyses for the final Week 24 analysis are included in this SAP.

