## 6.7. Study Day

For each subject, study day is calculated relative to Day 1, where Day 1 is defined as the date of first dose of study drug. If the date of interest occurs on or after Day 1, then the study day will be calculated as: date of interest – date of Day 1 + 1. If the date of interest occurs prior to Day 1, then the study day will be calculated as: date of interest – date of Day 1. For subjects who are randomized but never dosed, Day 1 will be defined as the subject's randomization date.

The nominal visit number for each visit, including scheduled, unscheduled, repeat, and early termination/end of study visits, will be re-mapped to an analysis visit according to [Table 4](#), [Table 5](#), [Table 6](#), [Table 7](#), [Table 8](#). If multiple measurements occur within the same visit window after mapping, the measurement that is closest to the target study day will be used for the summary tables where one observation per visit is needed, unless otherwise specified. Where there are ties between the earlier and later observation within the visit window, the earlier observation will be used. For the purpose of this study, months are defined as 4-week intervals.

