#### **9.5.5. Menstrual Regularity**

Menstrual regularity at Week 24 (in female subjects of childbearing potential who are not on hormonal or intrauterine device contraceptives) is a secondary endpoint. Subjects meeting these criteria were asked to input the dates for which they were assessing their menstrual cycle as well as the amount of flow (light [spotting], medium [normal flow], heavy [heavy flow with flooding or clotting]). For the purposes of this analysis, a menstrual cycle will be defined as two consecutive calendar days with any amount of flow. Menstrual cycle regularity is defined as a menstrual cycle every 21-35 days, translating to approximately 4 to 8 menstrual cycles from baseline to Week 24. The number and percentage of subjects meeting the definition for regular menstrual cycle at Week 24 will be summarized by treatment group. This summary will be stratified based on menstrual cycle regularity at study entry (as collected on the CAH medical history eCRF, “Do menstrual cycles typically occur every 21-35 days?”). This endpoint will be analyzed using a CMH test as described in Section 9.2.2. The CMH test will compare treatment groups and will include the stratification factors used in the randomization (with the exception of sex) as well as menstrual cycle regularity at study entry. The p-value from the CMH analysis will also be displayed in a table.

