## 10. EFFICACY – OL PERIOD

The efficacy endpoints and planned analysis methods for the OL period are described below. The OL Period Safety Analysis Set will be used for all efficacy analyses and descriptive statistics in the OL period. Unless otherwise noted, the below summaries will follow the treatment group and baseline definitions defined for the OL period (as described in Section 6). Missing data will not be imputed for any of the below analyses and summary displays will start with Month 7 as the first postbaseline visit, unless otherwise specified.

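### SAP 4.5 and 10.5: the open-label change in number of menstrual periods has no time denominator, so the Week 24 data cut would show a false fall or understate a gain

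*SAP*

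**What the plan says.** SAP 4.5 lists among the exploratory open-label endpoints the "change in number of menstrual periods (premenopausal female subjects assigned to the placebo group for the DB period", with users of hormonal or IUD contraception left out. SAP 10.5 describes the comparison: "number of menstrual periods from Week 24 to Month 12 will be compared to the number of menstrual periods from Day 1 to Week 24". It then adds: "The change in the number of menstrual periods between the two treatment periods will be summarized descriptively". Neither section mentions a rate, a denominator, a minimum time observed or a rule for a window that is not finished.

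Four other parts of the SAP decide how much open-label time each woman contributes:

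- **Analysis set.** SAP 10 states: "The OL Period Safety Analysis Set will be used for all efficacy analyses and descriptive statistics in the OL period". By SAP Table 1, one open-label dose of crinecerfont is enough to enter that set. SAP 10 also rules out imputation.
- **Timing.** At the Week 24 final analysis, SAP 5.2 says that "an analysis of all available safety and efficacy data through Month 12 will also be performed". SAP 1 names this as part of a planned milestone. SAP 5.3 then analyses the open-label period once all subjects have had the chance to reach Month 12.
- **Calendar.** SAP 6.7 states: "For the purpose of this study, months are defined as 4-week intervals".
- **Missing values.** SAP 6.6 makes a change missing when either value is missing. It does not say whether a count from an unfinished window is a missing value.

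**The concern.** A count of events grows with the time over which events are counted. A woman must have reached the open-label period to be in this set, so her first count covers roughly the full 168 days. Her second count covers whatever open-label time has been recorded by the analysis date. Truncation therefore falls almost entirely on one side of the subtraction and pushes the change downward.

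The summary describes, within the same woman, how menstruation differs between placebo time and crinecerfont time. A downward error runs against the benefit that the comparison would be expected to show, and it is largest in the earlier of the two planned reports.

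**Working it through.** **1. The plan's own figure.** SAP 9.5.5 counts as follows: "a menstrual cycle will be defined as two consecutive calendar days with any amount of flow". It equates a cycle every 21 to 35 days with a count, "translating to approximately 4 to 8 menstrual cycles from baseline to Week 24". Check: 168/21 = 8.0, and 168/35 = 4.8, or 4 whole cycles. The figure reproduces.

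**2. Nominal windows.** SAP Table 4 targets day 168 for Week 24 and day 336 for Month 12. The open-label window is 336 - 168 = 168 days, equal to the double-blind window.

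**3. Visit windows.** Protocol Section 7 allows ±5 days at Week 24 and ±7 days at Month 12. The extremes are 173 days then 329 - 173 = 156 days (difference -17), or 163 days then 343 - 163 = 180 days (difference +17). At a 28-day cycle this is 17/28 = 0.6 period in either direction.

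**4. One woman whose cycle does not change.** Raw change = (open-label days - 168) / cycle length, in expected counts:

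| Open-label weeks observed | 21-day cycle | 28-day cycle | 35-day cycle |
|---|---|---|---|
| 4 | -6.7 | -5.0 | -4.0 |
| 8 | -5.3 | -4.0 | -3.2 |
| 12 | -4.0 | -3.0 | -2.4 |
| 16 | -2.7 | -2.0 | -1.6 |
| 20 | -1.3 | -1.0 | -0.8 |
| 24 | 0 | 0 | 0 |

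**5. Cohort mean at the Week 24 analysis.** Assumptions: uniform accrual over R weeks, a data cut when the last subject reaches Week 24, no withdrawal, and unchanged 28-day cycles. R is not in the documents, so a range is shown. Women enrolled in the last 24 weeks have incomplete open-label time, a share of 24/R, and they lack 12 weeks on average. The mean deficit over all women is 24 × 12/R = 288/R weeks, which at one period per 4 weeks is 72/R periods.

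| R (weeks) | Share incomplete, 24/R | Mean deficit, 288/R (weeks) | False mean change, -72/R |
|---|---|---|---|
| 52 | 46% | 5.5 | -1.4 |
| 78 | 31% | 3.7 | -0.9 |
| 104 | 23% | 2.8 | -0.7 |

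**6. Women with few or no periods on placebo.** Take a woman with 3 periods on placebo who moves to 28-day cycles. Over a full open-label window she shows 6 - 3 = +3; seen for 12 open-label weeks she shows 3 - 3 = 0. A woman with none on placebo shows +6 or +3 respectively. Her change cannot be falsely negative, but the gain is understated.

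**7. Cohort mean at the Month 12 analysis.** The data cut no longer truncates. If a share x leaves the study at uniform times in the open-label period, each loses 84 days on average, so the false change at a 28-day cycle is -x × 84/28 = -3x. This gives -0.15 for 5% and -0.30 for 10%. These shares are assumptions.

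**8. With a time base.** Periods per 28 days observed for an unchanged cycle are 1.33 (21-day), 1.00 (28-day) and 0.80 (35-day) in both windows. The expected change is 0 for any open-label length.

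**The case against.** The strongest reply is that the windows are equal by design and that the definitive open-label analysis in SAP 5.3 waits until everyone could have reached Month 12. Both statements are correct, and they confine the material error to the Week 24 data cut.

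The plan also does not say that an unfinished count is to be entered as though it covered the whole window, and SAP 5.2 does not name this display. That is fair as a matter of wording. But the SAP excludes elsewhere when it means to: SAP 6.3.2 drops six-monthly assessments that lack a Week 24 value. It has no such rule here, and a partial count is still a value under SAP 6.6. Followed as written, the plan includes these women.

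A reader might infer that any woman who stops study drug in the open-label period has a truncated count. The documents do not support that. Protocol 9.10 and 9.10.1 keep subjects who stop drug before Month 18 in follow-up, and Protocol 9.3.7 schedules diary review at Months 7, 8, 9, 10 and 12. Truncation after the data cut is removed needs study withdrawal, loss to follow-up or diary gaps.

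A reader might also treat this as a test, or as the only within-woman look at menstruation. It is neither. The summary is descriptive, and SAP 4.5 separately lists change from baseline in menstrual regularity at Month 12.

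**Conclusion.** The point holds in a limited form. The raw difference is fair, apart from visit windows of up to about 0.6 period either way, for women observed to Month 12. At the SAP 5.2 analysis it carries a predictable downward error: a mean of about 0.7 to 1.4 periods for unchanged 28-day cycles under uniform accrual over 104 to 52 weeks, against an expected 6 per window. Faster accrual would enlarge it; a lag between the last Week 24 visit and the data cut would shrink it. The range describes regular cyclers. Among women with few or no periods on placebo the effect is an understated gain.

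The stronger conclusion, that the Month 12 result is seriously biased, is not supported: with 5% to 10% withdrawal the error there is about 0.15 to 0.30 period. The endpoint is exploratory, limited to women first randomized to placebo, and has no bearing on the primary or key secondary results. This is a minor improvement.

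**What to change.** In SAP 4.5 and 10.5, express each count as periods per 28 days of diary-observed time in its own window, summarise the change in that rate, and show the days observed in each window beside it. Add a short rule for which days count as observed.

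No minimum observation time is required. Rates from very short windows will be noisy, which is why the days observed should be shown. If the sponsor prefers a minimum, the SAP should say that it may leave out a material share of women at the Week 24 cut. At 84 days (12 weeks), the same accrual model excludes 12/R: 12/52 = 23%, 12/78 = 15% or 12/104 = 12%.

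The cost is a sentence or two in each section and a denominator derived from dates. The eDiary has recorded dated flow since Screening Visit 1 (Protocol 9.3.7), so no new data are needed.

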## 10.6. TARTs

Change from baseline to Month 12 in TARTs will also be summarized for the OL period. For the purpose of summarization, the volume of each lesion will be used to assess size (in cubic millimeters) at visits where the testicular ultrasound is performed. Volume will be calculated using the following formula: volume = length x width x depth x 0.5236. The volume of each testicle will be calculated using the same formula. Descriptive statistics will be used to summarize the total TART volume (calculated as the sum of the volume of each lesion across both testes) for each subject by treatment group and visit. Observed and change from baseline values will be included in the summary table. Note that this summary will be repeated for the observed and change from OL baseline values.

Additionally, the total TART volume will be expressed as a percentage of the total testicular volume and calculated as the sum of the volume of each lesion across both testes divided by the total testicular volume across both testes for each subject. The total TART volume as a percentage of the total testicular volume will be summarized with descriptive statistics by treatment group and visit. Observed and change from baseline values will be included in the summary table. Note that this summary will be repeated for the observed and change from OL baseline values.

The number and percentage of subjects with the presence of TARTs, whether they are unilateral or bilateral, and the average number of TARTs per subject will be summarized with descriptive statistics by visit and treatment group. The number and percentage of TARTs with each shape, boundary, hypervascularity, calcification, and the echogenicity will be summarized with descriptive statistics by visit and treatment group.

A response assessment will be conducted at Month 12 for subjects with the presence of TARTs at baseline. Response categories and the criteria for each category are detailed in [Table 9](#) within Section 9.5.6. The frequency and percentage of subjects meeting each classification at Month 12 (as compared to baseline) will be summarized by treatment group.

## 10.7. Bone Mineral Density

BMD (assessed via DXA) will be summarized with descriptive statistics by visit and treatment group. Summary tables will include observed and change from baseline values for BMD (in  $\text{g}/\text{cm}^2$ ) for each region of measurement.

The number and percentage of subjects meeting criteria for normal BMD (T-score  $\geq -1.0$ ), osteopenia (T-score  $< -1.0$  to  $> -2.5$ ), or osteoporosis (T-score  $\leq -2.5$ ) will be summarized by visit and treatment group. Descriptive statistics for observed and change from baseline in BMD T-scores will also be summarized by treatment group by visit and region of measurement.

The above summaries will be repeated for the change from OL baseline to Month 12 in BMD.

## 10.8. Hirsutism and Acne

Visual analog scales (VAS) were used to assess the subject's perception of severity of hirsutism and acne in all female subjects, scored on a 100 mm visual analog scale from 0 mm (no symptoms) to 100 mm (very severe symptoms). Observed and change from OL baseline values in VAS scores for hirsutism and acne will be summarized descriptively by visit and treatment

group. Mean ( $\pm$ SEM) observed values at each visit will be summarized in line graphs by treatment group. Similar graphs will be presented for the change from OL baseline values.

The above summaries will be repeated for the change from baseline to Month 12 in VAS scores for hirsutism and acne.

## **10.9. Bone Markers**

Serum osteocalcin and serum bone-specific alkaline phosphatase are bone marker measurements to assess bone formation. Serum C-terminal telopeptide (CTX) and urine N-terminal telopeptide (NTx) are bone marker measurements to assess bone resorption. Observed and change from OL baseline values in these bone markers will be summarized using descriptive statistics by treatment group and visit. This summary will be repeated for the change from baseline to Month 12 by treatment group and visit.

## 11. SAFETY

The safety objective of the study is to characterize the safety and tolerability profile of crinecerfont as measured by TEAEs (including SAEs), clinical laboratory tests, vital signs, ECG, and neuropsychiatric assessments. All outputs for safety endpoints during the DB period will be based on the DB Period Safety Analysis Set. Safety data will be summarized descriptively by treatment group. All outputs for safety endpoints during the OL period will be based on the OL Period Safety Analysis Set and will be summarized descriptively by treatment group. Safety data will not be subject to any imputation and will be summarized on an observed case basis. No formal hypothesis-testing analysis of safety data will be performed. Unless otherwise noted, the below summaries will be produced for both the DB period and the OL period safety data separately and will follow the treatment-period specific treatment group and baseline definitions (as described in Section 6). All by-visit safety tables will also include a safety follow-up visit summary (as defined in [Table 5](#)) and subject data collected after the safety follow-up visit will not be summarized.

